**Flexibility in Dose Adjustment of Stage 1:**

[figure not shown]
In the first stage of the study, if an intolerable dose is identified (based on one of the above 5 criteria), a lower dose may be evaluated as proposed by the SRC. This lower dose may be a repeat of the prior lower dose cohort or an intermediary dose between the intolerable dose and prior lower dose cohort. If the dose is an intermediary dose, a sentinel group consisting of 2 subjects (1 active: 1 placebo) will be dosed first. The SRC will review all available safety

data of the prior sentinel group through at least Day 5 post-operatively, and 6 additional subjects (5 active: 1 placebo) will be dosed upon approval.

In addition, if the SRC deems appropriate, before an intolerable dose is identified, a repeat dose, or a dose not exceeding the planned dose of the next cohort may be evaluated.

If a repeat or lower dose (i.e., any dose at or lower than prior highest dose evaluated without meeting stopping criteria) is considered, subjects may be dosed without implementing sentinel dosing strategy.

All dose escalation/adjustments or additional cohorts and corresponding sample size will be determined by the SRC. [REDACTED]

## 4.2 Study Endpoints

### 4.2.2 Primary Efficacy Endpoint

- Area under the curve (AUC) of subject's assessment of pain using the Numeric Pain Rating Scale (NPRS) between 12 and 96 hours post-surgery (AUC12-96).

#### 4.2.3 Secondary Efficacy Endpoints

- AUC assessment of overall pain profile using NPRS:
  - Over the first 96 hours post-surgery ( $AUC_{0-96}$ )
  - Over the first 72 hours post-surgery ( $AUC_{0-72}$ )
  - Over the first 48 hours post-surgery ( $AUC_{0-48}$ )
  - Over the first 24 hours post-surgery ( $AUC_{0-24}$ )
  - Over the period of 12 to 24 hours post-surgery ( $AUC_{12-24}$ )
  - Over the period of time X to 96 hours post-surgery ( $AUC_{t-96}$ ), whereas X is any time during confinement
- Pain assessment at rest after discharge using NPRS at Days 6 through 29.
- Pain assessment after sitting up in the bed unassisted at an angle of approximately 45 degrees or more, swinging legs out, putting feet down, standing up, and walking approximately 10 feet using NPRS-A (NPRS administered after an activity) over the first 96 hours and at Days 8, 15, 29.
- Patient global assessment (PGA) of pain control
- Use of rescue medications over various postsurgical periods

### 5 STUDY ENROLLMENT AND WITHDRAWAL

Prior to shipment of study drug and before subjects may be enrolled in the study, the Sponsor or designee requires a copy of the following critical documents:

- Institutional Review Board (IRB) / Independent Ethics Committee (IEC) approval of the protocol and the subject Information Sheet / Informed Consent Form (ICF);
- Signed and dated protocol signature page;
- Completed Food and Drug Administration (FDA) Form 1572 (central laboratories and any local laboratories for the study must be listed on the form);
- Up-to-date curricula vitae and medical licenses (if applicable) of the Principal Investigator (PI) and all Sub-Investigators listed on the FDA Form 1572;
- Signed financial disclosure forms for the Principal Investigator (PI) and all Sub-Investigators listed on the FDA Form 1572;
- Name, address, and membership of the IRB/IEC;
- Laboratory normal ranges and documentation of laboratory certification (or equivalent);
- Signed clinical study agreement;

All subjects must personally sign and date an IRB-approved ICF before any study procedures, including screening procedures, are performed. Subjects will be considered enrolled into the study only when they have received study drug.

## 5.1 Participant Inclusion Criteria

In order to be eligible to participate in this study, an individual must meet ALL of the following criteria:

1. Men or women 23 to 55 years of age, inclusive
2. Men or women who are in good health as determined by medical history, physical examination, clinical laboratory studies, ECGs, vital signs, and Investigator judgment
3. Scheduled to undergo elective abdominoplasty surgery with full length plication from xyphoid to pubis, and removal of skin/fat flap under general anesthesia (endotracheal or otherwise) without liposuction
4. American Society of Anesthesiologist (ASA) Physical Class 1-2
5. Women of non-childbearing potential or postmenopausal (at least 12 consecutive months of amenorrhea)
6. Women of childbearing potential must not be pregnant, lactating, or planning to become pregnant during the study
7. Women of childbearing potential agreeing to use either:
  - a. a highly effective method of contraception with failures rates less than 1% per year such as implant, intrauterine device (IUD), or confirmed sterilization and sterilization procedure at least 3 months prior to the day of dosing
  - b. dual methods of contraception with overall failures rate less than 1% per year such as injectable, pill, patch, ring, and diaphragm from the day of dosing for 3 months (subjects using oral contraception must have initiated treatment at least 2 months prior to the day of dosing)
8. Men with partner(s) of childbearing potential agreeing to use dual methods of contraception from the day of dosing until 3 months afterwards, and to no sperm donation from day of dosing until 3 months afterwards.
9. Willing and able to complete protocol requirements and instructions, which includes completion of all required visits, procedures and in-clinic stays until the end of the study
10. Willing and able to sign and date IRB-approved informed consent
11. Able to speak, read, and understand the language of the informed consent form (ICF) and study questionnaires

## 5.2 Participant Exclusion Criteria

An individual who meets ANY of the following criteria will be excluded from participation in this study:

1. History of prior major abdominal surgery as judged by the investigator
2. Pre-existing lung disease that could impact subject safety in the opinion of the investigator
3. History of smoking within the past two years
4. Pre-existing disorders of the neuromuscular junction (myasthenia gravis, Eaton-Lambert syndrome, or amyotrophic lateral Sclerosis)

5. Any past or current medical condition that in opinion of investigator, puts subject at undue safety risk for surgical complications or for use of the investigational product
6. Unacceptable risk of deep vein thrombosis (DVT) as deemed by the investigator
7. Past major surgery (more than 45 minutes) within the last 6 months
8. History of blood clots, either DVT or pulmonary embolism
9. Current or past malignancies (excluding skin cancer, but not melanoma) within the last 12 months
10. History of diabetes
11. Any clinically significant psychiatric condition that, in opinion of investigator, may interfere with study assessments or protocol compliance
12. History of alcohol or drug abuse in the last 3 years, based on investigator judgement
13. Slow vital capacity that is below 80% of normal value for respective race, age, height, and gender or below 2.5 L of absolute volume
14. Pulse oximetry below 95%
15. Body weight less than 50 kg (110 pounds) or a Body Mass Index (BMI) of  $\geq 32$
16. Documented diagnosis of chronic pain condition, or other painful pre-operative condition that, in the opinion of the investigator, may require analgesic treatment in the post-operative period (e.g. significant joint pain, neuropathic pain)
17. Known hypersensitivity to any botulinum toxin serotype or to any component of the formulation
18. Reported use of any botulinum toxin within 3 months prior to the date of surgery
19. Anticipated use of any botulinum toxin of any serotype during the study
20. Use of long acting opioids within 3 days or any opioid medication within 24 hours prior to surgery
21. Aminoglycoside intake within 48 hours prior to or during surgery
22. Use of anti-depressant or anti-psychotic medications in the past 3 months
23. Current enrollment in an investigational drug or device study or participation in such a study within 30 days or 5 half-lives of the drug, whichever is longer, of entry into this study
24. Subject plans to donate blood or plasma from 30 days prior to screening until last follow-up visit (Day 29)
25. Reported pain score of 2 or more at screening on the 11-point scale NPRS-A after walking approximately 10 feet

### 5.3 Strategies for Recruitment and Retention

A sufficient number of subjects will be screened to allow for approximately 90-98 eligible subjects to be randomized at up to 2 US-based investigational sites.

If radio, local print advertising, or any recruitment material is considered, prior Sponsor and IRB approval will be obtained. Potential subjects will be contacted via telephone for a preliminary screen of some of the inclusion and exclusion criteria. Only subjects who are able to provide voluntary, signed written informed consent will be admitted. Preliminarily

eligible subjects will be invited to the clinic for complete screening, as set forth in the Schedule of Study Procedures.

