**Investigational (Study) Sites:**

It is expected that up to 2 clinical surgical sites will conduct the study and enroll approximately 90-98 subjects.

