## 4 STUDY DESIGN AND ENDPOINTS

### 4.1 Description of the Study Design

This will be a two-stage study. The study will be conducted at up to two surgical centers that specialize in elective abdominoplasty surgeries and enroll up to 39-57 subjects in Stage 1 and 66 subjects in Stage 2 ([Figure 1](#)), with up to 67-82 subjects exposed to active drug. The study will include a screening visit to determine subject eligibility. On the day of surgery, subjects will be admitted to an inpatient clinic for 5 days post-operatively (Days 1-5) ([Table 1](#) and [Table 2](#)). Intraoperatively, a single dose of EB-001 IM will be given via IM injections into the RA muscles per the surgical procedure manual. Follow up visits will be scheduled at days 8, 15, and 29.

The first stage will be a placebo controlled, single-blind (to subject and staff at study sites), single ascending cohort study stratified by ethnicity (Hispanic and non-Hispanic) starting from Cohort 2. Six cohorts (3-8 subjects per cohort) will be dosed at 6 ascending doses of EB-001. An optional Cohort 7 may be considered.

Cohort 1 sentinel group (3 subjects; 1 active: 2 placebo) [REDACTED] The rest of the cohort (5 subjects; 3 active: 2 placebo) will be dosed at the same dose after review of all available data by the Safety Review Committee (SRC) is conducted, with safety data through at least Day 5 post-operatively.

Cohort 2 sentinel group (3 subjects; 1 active: 2 placebo) [REDACTED] after review of all available safety data from the prior cohort through at least Day 5 post-operatively. The rest of the cohort (5 subjects; 3 active: 2 placebo) will be dosed after review of all available data by the SRC is conducted, with safety data through at least Day 5 post-operatively.

Cohort 3 sentinel group (3 subjects; 1 active: 2 placebo) [REDACTED] after review of all available safety data from the prior cohorts through at least Day 5 post-operatively. The rest of the cohort (5 subjects; 3 active: 2 placebo) will be dosed after review of all available data by the SRC is conducted, with safety data through at least Day 5 post-operatively.

Cohort 4 group (5 subjects; 4 active: 1 placebo) [REDACTED] after review of all available safety data from the prior cohort through at least Day 5 post-operatively.

Cohort 5 group (3 subjects; 2 active: 1 placebo) [REDACTED] after review of all available safety data from the prior cohort through at least Day 5 post-operatively.

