**Investigational (Study) Sites:**

It is expected that up to 2 clinical surgical sites will conduct the study and enroll approximately 105-123 subjects.

[REDACTED]

[REDACTED]

[REDACTED]

[figure not shown]

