#### **5.5 Replacement of Subjects**

Up to 4 (or up to 1 subject per cohort) subjects in Stage 1 who discontinue from the study may be replaced (unless the discontinuation is due to one of the toxicity criteria in [Section 4.1.1](#) when subjects will not be replaced). Up to 9 subjects (or up to 3 subjects per cohort) in Stage 2 who discontinue from the study will be replaced (unless the discontinuation is due to safety reasons when subjects will not be replaced).

[figure not shown]

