## 10.5 Sample Size

Subjects will be allocated to receive either EB-001 or placebo in a 1:1 ratio in Cohorts 1-3, a 4:1 ratio in Cohort 4, a 2:1 ratio in Cohort 5, a 3:1 Ratio in Cohort 6, and a 5:1 ratio in Optional Cohort 7 in Stage 1 stratified by ethnicity (Hispanic and non-Hispanic) starting from Cohort 2. The planned total sample size in Stage 1 will be up to 40-58 subjects (up to 24-39 for EB-001 and up to 16-19 for placebo) (Figure 1). Optional Cohort 7 will be considered after dosing of subjects in Cohorts 1-6.

Subjects in each arm of Stage 2 will be randomly allocated to receive either EB-001 or placebo. The planned total sample size will be 66 subjects (44 for EB-001 and 22 for placebo) in Stage 2 stratified by ethnicity (Hispanic and non-Hispanic) (Figure 1).

Sample size of this study is not based on formal computations. However, 22 for active and 22 for placebo provide ~67% power. This power is based on one-sided alpha of 0.05, a mean baseline maximum pain score of 7.5, AUC12-96 ~440 with no drug effect, the delta AUC of 110 (drug and placebo difference), and SD of 170 AUC12-96.

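### The stated total of approximately 90-98 subjects does not match the current design, whose own cohort and stage sizes sum to 106-124

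*Protocol*

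**What the plan says.** The protocol states the planned size of the trial in several places.

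- **Total, Protocol Summary (Investigational Sites):** the sites will "conduct the study and enroll approximately 90-98 subjects".
- **Total, Section 5.3:** "A sufficient number of subjects will be screened to allow for approximately 90-98 eligible subjects to be randomized".
- **Total, Section 4.1 (Investigational Sites):** the sites will "enroll approximately 105-123 subjects".
- **By stage, Section 4.1:** the study will "enroll up to 39-57 subjects in Stage 1 and 66 subjects in Stage 2", "with up to 67-82 subjects exposed to active drug".
- **Stage 1, Section 10.5 (also the Summary's sample size text):** "The planned total sample size in Stage 1 will be up to 40-58 subjects", made up of 24-39 on EB-001 and 16-19 on placebo.
- **Stage 2:** 66 wherever it is given, split in Section 10.5 as 44 on EB-001 and 22 on placebo.
- **Replacements, Section 5.5:** "Up to 4 (or up to 1 subject per cohort) subjects in Stage 1" may be replaced, and up to 9 in Stage 2.

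Section 4.1 also lists the size and allocation of every Stage 1 cohort, so the totals can be checked directly.

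**The concern.** One design should have one planned total. Here the Summary disagrees with itself: its sample size text (40-58 plus 66) cannot be reconciled with the 90-98 in its sites paragraph. Section 5.3, which tells the sites how many subjects to screen for, carries the same low figure, while Section 4.1 carries a higher one. The Summary and the recruitment section are where sites and the IRB are likely to look for the total, so planned enrolment is understated there. If recruitment were planned to 90-98 and not revised, Stage 2 would be the part left short, because it comes last.

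**Working it through.** **1. Stage 1 from the cohort list in Section 4.1**

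| Cohort | Active | Placebo | Total |
|---|---|---|---|
| 1 | 1+3 = 4 | 2+2 = 4 | 8 |
| 2 | 4 | 4 | 8 |
| 3 | 4 | 4 | 8 |
| 4 | 4 | 1 | 5 |
| 5 | 2 | 1 | 3 |
| 6 | 1+5 = 6 | 1+1 = 2 | 8 |
| **1-6** | **24** | **16** | **40** |
| 7 (optional) | 15 | 3 | 18 |
| **1-7** | **39** | **19** | **58** |

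This reproduces Section 10.5 exactly.

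**2. Whole study**

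- Total: 40 + 66 = 106; 58 + 66 = 124.
- Exposed to EB-001: 24 + 44 = 68; 39 + 44 = 83.

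**3. The 105-123 in Section 4.1**

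This is that section's own sum: 39 + 66 = 105 and 57 + 66 = 123. Its 67-82 exposed is likewise one below 68-83. The one-subject difference is reproduced if Cohorts 1-3 are counted as 23 instead of 24: 23 + 5 + 3 + 8 = 39, and 39 + 18 = 57. SAP Section 2.4.3 reports 23 subjects randomized by the time Cohort 3 enrolment was complete, so an actual count may have been used. That is an inference; the protocol does not say it.

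**4. The 90-98**

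- Against the sums: 106 − 90 = 16 and 124 − 98 = 26, which is 15% and 21% low.
- Left for Stage 1 once 66 are set aside: 90 − 66 = 24 and 98 − 66 = 32, both below the 40 in Cohorts 1-6.
- 24 and 32 are three and four cohorts of 8. The amendment log fits this: before Amendment 3, Stage 1 had three cohorts and an optional cohort of 8. The figure therefore looks like one that was not updated, but this too is an inference.

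**5. What would follow if recruitment were held to 90-98**

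Inputs from Section 10.5: difference 110, SD 170, one-sided alpha 0.05, two groups of n. The noncentrality is 110 / (170 × √(2/n)), with 2n − 2 degrees of freedom.

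The plan's own case comes first. At n = 22 the noncentrality is 110 / 51.26 = 2.15, and power is 68.0% by noncentral t (69.2% by the normal approximation), against the stated ~67%.

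| Total | Stage 1 | Left for Stage 2 | Short of 66 | Per arm | Power |
|---|---|---|---|---|---|
| 98 | 40 | 58 | 8 | 19.3 | 63% |
| 90 | 40 | 50 | 16 | 16.7 | 57% |
| 98 | 58 | 40 | 26 | 13.3 | 49% |
| 90 | 58 | 32 | 34 | 10.7 | 42% |

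Using 39-57 for Stage 1 instead leaves 33-59, still below 66.

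**6. Replacements**

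One per cohort allows 6 replacements over six cohorts or 7 over seven, against the other stated limit of 4. With 4 in Stage 1 and 9 in Stage 2, the number randomized could reach 106 + 13 = 119 to 124 + 13 = 137, further from 90-98.

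**The case against.** The strongest defence is that 90-98 is only a recruitment estimate. Section 5.3 concerns how many to screen. Nothing in the protocol closes Stage 2 when a cumulative total is reached, and Stage 2 is given as 66 every time. Stage 1 is worded as a maximum, so 66 would fit within 90-98 if Stage 1 ended at 24-32. This stands as regards the consequence. A reader might infer that the trial could not supply its 66 Stage 2 subjects; the documents do not support that. The defence does not rescue the figure itself. A Stage 1 of 24-32 is not the planned one, and the word approximately does not stretch to a gap of 15-21%.

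A reader might also measure the loss with the Dunnett comparison named in Section 10.4.2. On that basis per-dose power is about 58% even with all 66 subjects. The drop from 68% to 58% comes from the multiplicity adjustment and not from the enrolment figure. The protocol's own power statement is unadjusted, so that is the basis for sizing this point. The protocol also says that the sample size does not rest on formal computations.

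The 39-57, 105-123 and 67-82 might be read as further errors of the same kind. They agree with one another, differ from the cohort sums by one subject, and may reflect an actual count.

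Nor can 90-98 be read as misstating exposure to active drug, which Section 4.1 gives separately. The SAP's 32-74 for Stage 1 is not another conflict, because the SAP is based on Amendment 3.

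**Conclusion.** The 90-98 in the Summary and Section 5.3 is wrong for the current design by 16 subjects at the lower end and 26 at the upper. This rests only on the protocol's cohort list and Stage 2 size, with replacements left out. That the figure survives from a smaller design is likely but inferred.

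The effect on Stage 2 is conditional. If recruitment were held to 90-98 after a full Stage 1 of 40-58, Stage 2 would be 8-34 short and power would be 42-63% against 68%. No passage requires recruitment to stop there.

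The one-subject difference between Section 4.1 and Section 10.5, and the two Stage 1 replacement limits, are minor and need only reconciling. The SAP reports that the study ended after 23 subjects in Stage 1 and that no statistical comparisons will be made. The defect is therefore in the consistency of the plan and not in any result.

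**What to change.** Replace 90-98 with 106-124 in the Protocol Summary (Investigational Sites) and in Section 5.3. Then use one Stage 1 basis in the Summary, 4.1, 5.3 and 10.5:

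- **either** the planned cohort sizes: Stage 1 40-58, total 106-124, exposed to EB-001 68-83;
- **or**, if Section 4.1 counts 23 subjects already enrolled in Cohorts 1-3, say so and use 39-57, 105-123 and 67-82 in all four places, including the two that now read 90-98.

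State the Stage 1 replacement limit in Section 5.5 as a single rule that agrees with six or seven cohorts, and say whether the totals include replacements.

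The cost is a text correction. The design and the analysis do not change.

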## 5.4 Participant Withdrawal or Termination

### 5.4.1 Reasons for Withdrawal or Termination

Participants are free to withdraw from participation in the study at any time upon request for any reason without prejudice to his or her future medical care by the physician or at the institution. A subject may be terminated from the study for any of the following reasons:

- Withdrawal of informed consent.
- Entry into the study in violation of the protocol.
- Any AE, laboratory abnormality, or other medical condition or situation occurs such that the study doctor or study staff believes continued participation in the study would not be in the best interest of the participant.
- The participant meets an exclusion criterion (either newly developed or not previously recognized) that precludes further study participation.
- Noncompliance with the protocol (except for exceeding limit of allowed rescue medication; specified below in [Section 5.4.3](#)).
- At the discretion of the Investigator or Sponsor for any reason.

### 5.4.2 Handling of Participant Withdrawal or Termination

If a subject discontinues from the study prematurely, all efforts will be made to conduct early termination (ET) evaluations as thoroughly as possible up to the date of withdrawal at the time of discontinuation.

Subjects who discontinue participation, or who are discontinued prior to completing study participation, will be asked to complete ET procedures, including:

- Assessment of AEs
- Assessment of AEs of Special Interest including post-operative dyspnea, tachypnea, tachycardia, pneumonia, atelectasis, and fever
- Height, weight, and BMI
- Mini-physical and focused neurological examinations
- Prior and concomitant medications
- 12-lead ECG
- Body temperature, respiration rate, blood pressure, pulse oximetry, and pulse rate
- Serum chemistry, Lipids, and Hematology
- Urinalysis
- Immunogenicity sample collection
- Pregnancy test
- Postoperative wound assessment

- Overall assessment of pain at rest using NPRS (if prior to the 96-hr assessment)
- Pain assessment using NPRS-A after sitting up in the bed unassisted at an angle of approximately 45 degrees or more, swinging legs out, putting feet down, standing up, and walking approximately 10 feet (if prior to the 96-hr assessment)
- Patient global assessment (PGA) of pain control
- Pulmonary function test (SVC, FVC, and FEV1)
- Use of rescue medications
- Collection of take-home diaries (if applicable)

#### **5.4.3 Handling of Participant Exceeding Allowed Rescue Medication**

Subjects who exceed limit of allowed rescue medication, considered noncompliance with the protocol specified in [Section 5.4.1](#) due to lack of efficacy, will be followed, not early terminated, with regard to all safety assessments per protocol. They at all subsequent visits will be asked to complete protocol-specified assessments, with the exception of efficacy assessments as follows:

- NPRS
- NPRS-A
- Collection of take-home pain assessment diary

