**Efficacy Measures: Primary**

**Efficacy Measures:**

- Area under the curve (AUC) of subject's assessment of pain using the Numeric Pain Rating Scale (NPRS) between 12 and 96 hours post-surgery ( $AUC_{12-96}$ ).

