If a subject requests rescue medication, the pre-rescue pain NPRS and NPRS-A assessments will be carried forward for 4 hours. Handling of missing data for subjects who discontinue the study will be specified in the SAP.

[figure not shown]

[REDACTED]

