### **10.3 Analysis Populations**

The modified Intent to Treat (mITT) population will include all randomized patients who receive study drug. All efficacy analyses will be performed using this population. Analyses will be performed on subjects using their randomized treatment group.

The Per Protocol (PP) population will include all subjects in the mITT population with no major protocol violations. The primary efficacy variable will also be analyzed using this population.

The Safety population will include all subjects exposed to any amount of study drug. All safety analyses will be performed using the safety population.

Analyses of using the PP and Safety populations will analyze subjects according to the treatment received. In the event that the subject receives the wrong treatment, they will be excluded from the per protocol population.

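### Pain scoring stops by rule once a subject exceeds the rescue limit, and the SAP then sums the shortened AUC12-96 without rescaling

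*Protocol*

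**What the plan says.** - **Who is affected.** Protocol 5.4.3 concerns people who go over the rescue allowance, which it classes as a form of noncompliance. On cause and follow-up it reads: "due to lack of efficacy, will be followed, not early terminated, with regard to all safety assessments per protocol".
- **What stops.** The same section continues: "They at all subsequent visits will be asked to complete protocol-specified assessments, with the exception of efficacy assessments as follows". The list is NPRS, NPRS-A and collection of the take-home pain diary. The patient global assessment and rescue use are not on it.
- **Primary endpoint.** Protocol 4.2.2: "Area under the curve (AUC) of subject's assessment of pain using the Numeric Pain Rating Scale (NPRS) between 12 and 96 hours post-surgery". Protocol 7.1.1.25 schedules NPRS every 2 hours until discharge, and the Protocol Summary puts discharge at 96 hours.
- **Contrast.** Subjects who terminate early are still asked for "Overall assessment of pain at rest using NPRS (if prior to the 96-hr assessment") under Protocol 5.4.2.
- **Missing data.** After rescue, "the pre-rescue pain NPRS and NPRS-A assessments will be carried forward for 4 hours" (Protocol Summary). The Protocol Summary leaves other missing-data handling to the SAP, but only for subjects who discontinue the study.
- **SAP handling.** Section 3 treats a subject with inadequate relief who takes rescue outside the protocol as discontinued from efficacy from that time. Section 7.1.1 repeats the 4-hour carry-forward after protocol-specified rescue, imputes nothing else after early drop-out, and bases the AUC on non-missing values. Section 7.3.1 gives a plain trapezoidal sum with no scaling to the full window.
- **Population.** In Protocol 10.3 the mITT population is all randomized subjects who receive study drug: "All efficacy analyses will be performed using this population". SAP 4.1 adds a requirement for at least one NPRS between 12 and 96 hours.
- **Status.** SAP 1 and 2.2 report early termination after 23 randomized subjects, with descriptive summaries only.

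**The concern.** The subjects whose pain was worst controlled are the ones whose pain is no longer measured. The missingness is triggered by the outcome, and it occurs in people who remain under observation: they are inpatients through Day 5 and their safety assessments continue. A subject who leaves the study is asked for one more NPRS, while a subject who stays is not.

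Nothing downstream repairs this. These subjects do not discontinue the study, so the protocol's deferral to the SAP does not cover them. The SAP sums whatever intervals remain. Because AUC grows with observed time, a shortened record gives a smaller AUC, and smaller means less pain. The result can be worse than a blank value, because a failure may be scored as a good responder and averaged in with the rest of the arm.

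**Working it through.** **1. The plan's own figure.** Inputs from Protocol 10.5: 22 per arm, difference 110, SD 170, one-sided alpha 0.05, placebo AUC12-96 about 440. Noncentrality = 110 / (170 × √(2/22)) = 2.15 on 42 df, which gives power of 68.0% against the stated ~67%. The inputs reproduce. The planned active mean is 440 − 110 = 330. Over 84 hours the means correspond to average NPRS of 440/84 = 5.24 and 330/84 = 3.93.

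**2. One subject.** Assume constant pain of 8, with scoring stopping at hour T. The true AUC12-96 is 8 × 84 = 672. The summed AUC is 8 × (T − 12), or 8 × (T − 12 + 4) if the carry-forward applies. Both are shown because the SAP ties the carry-forward to protocol-specified rescue and does not say whether the dose that breaches the limit counts.

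| Stop at | Window lost | Summed AUC | With 4 h carry-forward |
|---|---|---|---|
| 24 h | 72/84 = 86% | 96 | 128 |
| 48 h | 48/84 = 57% | 288 | 320 |
| 72 h | 24/84 = 29% | 480 | 512 |

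Stops at 24 and 48 hours both score below the planned active mean of 330. At 24 hours this holds whatever the pain: even a constant 10 gives only 10 × 12 = 120, or 10 × 16 = 160. At 48 hours it holds for constant pain up to 330/36 = 9.2, or 330/40 = 8.25 with carry-forward.

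**3. Difference between arms.** The documents give no excess rates, so assume 20% on placebo and 10% on active, all at constant pain 8. Apparent difference = 110 − (0.20 − 0.10) × 8 × (96 − T), with 4 hours fewer lost under carry-forward.

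| Stop at | Without carry-forward | With carry-forward |
|---|---|---|
| 24 h | 52.4 | 55.6 |
| 48 h | 71.6 | 74.8 |
| 72 h | 90.8 | 94.0 |

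With equal rates, pain and timing in both arms the difference stays at 110. With the rates swapped, the loss changes sign: a stop at 24 hours gives 110 + 57.6 = 167.6, or 164.4 with carry-forward.

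**4. Power, as illustration.** 40,000 simulated two-arm trials used the protocol's means and SD, with AUC limited to 0–840, a pooled one-sided t-test and no carry-forward. A subject was assumed to fail at a mean NPRS of 7 or more, which is about 19% of placebo and 6.5% of active.

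| Handling | Mean difference | Power |
|---|---|---|
| NPRS collected to 96 h in everyone | 108 | 68% |
| Failures left out | 74 | 49% |
| Summed, stop at 24 h | 33 | 17% |
| Summed, stop at 48 h | 58 | 42% |
| Summed, stop at 72 h | 83 | 63% |

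For cut-offs from 6.5 to 7.5, power is 43% to 54% with failures left out and 10% to 64% with shortened sums.

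**5. Population.** A subject whose scoring stops before 12 hours has no NPRS in the window. That subject is in the mITT population of Protocol 10.3 but not in that of SAP 4.1.

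**The case against.** **Scope.** Section 5.4.3 speaks of subsequent visits, and elsewhere visits often means Days 8, 15 and 29. If only those were meant, AUC12-96 would be untouched. This stands as a caution: the inpatient reading is an inference. It is supported by NPRS being listed separately from the take-home diary, and by SAP 3 removing rescue failures from the efficacy portion with effect on the analgesic endpoints. Protocol 7.2, where the table of contents places rescue use, is not in the public text and might settle it.

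**What is lost.** A reader might infer that the whole primary endpoint is left missing on purpose. The documents do not support that. Scores before the excess are kept, an excess after 96 hours does not touch AUC12-96, and no motive is stated. Rescue use and the global assessment continue, and SAP 4.3 and 7.3.4 report efficacy discontinuations and all rescue taken, so failures remain visible.

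**Analysis options.** A reader might also infer that no valid analysis is possible. A composite that assigns a failure value needs only the fact and time of failure. It is a treatment-policy analysis, using pain scores regardless of rescue, that cannot be done without the later scores.

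**Consequence.** The study was not formally powered, stopped after 23 subjects, and will have no statistical comparisons. That limits the practical effect but does not remove it: SAP 7.3.1 still lists individual AUCs, SAP 3 summarizes continuous assessments by treatment, and the protocol still describes a 66-subject Stage 2 with hypothesis tests.

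**Conclusion.** The concern holds for scores after the excess. Followed as written, protocol and SAP together make NPRS missing because of poor pain control, and can then turn the gap into a falsely low AUC12-96. The single-subject result (672 true, against 96–128 at 24 hours and 288–320 at 48 hours) rests on constant pain of 8 and on the inpatient reading of 5.4.3.

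The effect on the arm difference and on power depends on assumed rates and timing of excess. The ranges in the working are illustrations, not estimates for this trial. It is tempting to say the rule must work against EB-001 because placebo subjects will exceed the limit more often. That presumes efficacy. With more excess on EB-001 the bias would favor the drug, and with equal rates, pain and timing the difference would not move.

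It would also be too strong to say that these subjects always stay in the mITT population, given the SAP's entry rule. Nor do the documents show that any of the 23 subjects exceeded the limit.

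**What to change.** - **Protocol 5.4.3:** delete the exception for NPRS, NPRS-A and the pain diary, so that scheduled scores continue to 96 hours and the diary to Day 29 regardless of rescue use. Record the time at which the limit was exceeded.
- **Protocol 5.4.3 and SAP 3:** reconcile the triggers. The protocol uses exceeding the allowed amount; the SAP uses rescue outside the protocol. The SAP is written to Amendment 3, so the alignment should be to the current protocol.
- **SAP 7.1.1 and 7.3.1:** state that a truncated AUC is not summed as if complete, and prespecify how rescue failures are handled, with a sensitivity analysis. Which strategy is primary is for the sponsor to choose.
- **SAP 4.1:** say how subjects whose scoring stopped before 12 hours are reported.

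The rescue rules themselves are not touched. The cost is a short protocol edit, some SAP text and a small added burden on subjects. They are already inpatients to 96 hours and already followed for safety, so no visits are added.

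For the 23 subjects already dosed, only the SAP handling and the flagging of truncated AUCs in listings and summaries can still be changed. The collection change applies to any further enrollment under the protocol.
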